13.2.1. Disease control

Disease control will be based on whether 17-OHP levels are in the optimal range and also whether the A4 levels are in the normal range (both analysed separately), see

Table 8. A subject will be considered a responder (i.e. disease controlled) if their 09:00 results are in the optimal range for 17-OHP and then separately if their 09:00 results for A4 are in the normal range. The number and percentage of subjects achieving 17-OHP and A4 results in the optimal and normal range respectively, will be presented at each visit by feeder study and previous treatment. This will be repeated for the 13:00 values.

The number and percentage of subjects achieving a 17-OHP concentration of <36.4 nmol/L at 09:00 will be summarised at each visit overall and by feeder study and previous treatment.

Table 8: Optimal range for 17-OHP and normal reference range for A4.

17-OHP#	1.2- 36.4 nmol/L
Androstenedione (A4)*	Males: 1.4 – 5.2 nmol/L
	Females: 1.0 – 7.0 nmol/L

Source:

* 17-OHP: Note the Mayo Clinic laboratory normal ranges for 17-OHP were derived from a very small number of volunteers, who did not have CAH and for whom nothing else was known, e.g. time of day, comorbidities. The appropriateness of trying to drive the CAH population into this range is questionable and therefore based on verbal feedback from clinicians who manage these patients, a broader "optimal range" has been used for 17-OHP.

*Mayo Clinic.

A4: http://www.mayomedicallaboratories.com/test-catalog/Clinical+and+Interpretive/9709

Exploratory analyses will also be undertaken to assess the relationship between disease control and the proportion of daily dose given at night. A summary of the number and percentage of responders will be produced by proportion of daily dose given at night, previous treatment, feeder study and overall DIUR-006 study. The proportion of daily dose given at night will be split into the following categories:

- <=30%
- >30% <=50%
- >50% <= 70%
- >70% <=90%
- >90%

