#### Blood samples

Will be taken by suitably qualified study personnel for:

- o routine safety laboratory tests (see Appendix 1).
- o measurement of serum CTX, osteocalcin, hsCRP, HbA1c, testosterone, fasting insulin and glucose. The fasting samples should be taken as soon as possible after the subject arrives for the visit before any food is consumed.
- o measurement of PRA after the subject has been supine for 30 minutes
- o blood samples will be taken at 09:00 and 13:00 hours for testing of 17-OHP and A4 levels.
- A blood sample for genotyping will be obtained, if necessary, from subjects entering from study DIUR-003, but if previous genotyping has been performed the patient will be asked for their permission for this information to be taken from their medical records and recorded in the eCRF.

To minimise the risk of anaemia associated with the withdrawal of multiple blood samples for laboratory testing, the planned blood volume to be drawn at each visit will be limited to a maximum of 49 mL. The date and time of collection of all blood samples will be recorded in the subject's eCRF. Copies of laboratory accreditation certificates and reference ranges will be provided prior to the analysis of the first subject sample.

All laboratory analyses will be carried out by the central laboratory results are needed urgently for safety reasons during the study, these can be processed at the local laboratory but the results must be recorded in the eCRF.

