#### 11.11 COVID-19 Procedures

Appropriate measures have been put in place to enable the study to continue during the COVID-19 restrictions. Therefore, if necessary, visits can be performed remotely (via telephone or video call) and IMP shipments can be made directly to the subject's home. Safety and endocrine blood sampling can also be performed locally if required (which could include nurses/phlebotomists performing home visits or subjects attending local doctor/general practitioner's office, local endocrinologist's office and local patient centres or clinics) for scheduled 6-monthly visits and dose titrations, to maintain patient safety and consideration of local environmental factors. If local laboratories are used, then normal ranges and certification of the local laboratories will be required. However, prior to implementation of any of these measures Sponsor approval must be obtained.

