9.2.2. Derivations of SDS scores

As part of the secondary objectives, the change from pre-Chronocort® baseline (see Section 9.3.2) in SDS of 17-OHP and A4 will be calculated. The SDS is defined as the absolute (unsigned) number of standard deviations above or below the average of the lower and upper limit of normal.

For each of the 17-OHP and A4 concentrations at each visit at each time point (09:00, 13:00), the natural logarithm will be taken and the SDS will be calculated by counting the number of standard deviations which are above or below the mean of the log transformed range (given in Table 3). The mean of the SDS scores for each androgen will be calculated over the two timepoints. Missing values will be handled as described in Section 9.1.

Table 2: Normal reference ranges for 17-OHP and A4

	Male	Female
17-OHP	1.2* – 6.7 nmol/L	1.2* – 8.6 nmol/L
A4	1.4 – 5.2 nmol/L	1.0 – 7 nmol/L

Source: Mayo Clinic.

17-OHP: http://www.mayomedicallaboratories.com/test-catalog/Clinical+and+Interpretive/9231.

Please note the upper reference range for females is during the luteal phase.

Table 8) will be used in the derivation of the average SDS score. This will enable calculation of an 'unsigned' SDS score which can be used to assess potential overtreatment as well as undertreatment.

A4: http://www.mayomedicallaboratories.com/test-catalog/Clinical+and+Interpretive/9709

^{*}There is no lower reference range available for 17-OHP, hence the lower limit of the optimal range (provided in

Statistical Analysis Plan

Version: 6.0 12 July 2022

Table 3: Mean and SD of normal log-transformed range

Analyte	Sex	mean of log _e -transformed range [log _e (nmol/L)]	SD of log _e -transformed range [log _e (nmol/L)]
17-OHP	Male	1.042	0.430
	Female	1.167	0.492
A4	Male	0.993	0.328
	Female	0.973	0.486

Source: Mayo Clinic.

17-OHP: http://www.mayomedicallaboratories.com/test-catalog/Clinical+and+Interpretive/9231.

Please note the upper reference range for females is during the luteal phase.

A4: http://www.mayomedicallaboratories.com/test-catalog/Clinical+and+Interpretive/9709

The mean of the "normal" log-transformed range was calculated by averaging the natural logarithm of the upper and lower limit given in Table 2. The SD of the log-transformed range was approximated by dividing the range of the log-transformed values by four.

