11.4.2. Haematology

The following haematology parameters will be collected:

Red blood cell count (RBC), red cell distribution width (RDW), haemoglobin (Hb), haematocrit (Hct), mean corpuscular volume (MCV), mean cell haemoglobin (MCH), mean cell haemoglobin

Version: 6.0 12 July 2022

concentration (MCHC), platelet count (PLT), white blood cell count (WBC), WBC differential count: neutrophils, eosinophils, basophils, lymphocytes, monocytes (absolute).

All laboratory analyses will be carried out by the central laboratory. If laboratory results are needed urgently for safety reasons during the study, these can be processed at the local laboratory and the results recorded in the electronic case report form (eCRF). For the local lab data, the local reference ranges will be used and if for any reason these are missing, the central ranges will be used, with any such occurrences clearly marked in the listings. Change from pre-Chronocort® baseline (see Section 9.3.2) will be calculated at each visit (every 6 months from baseline) and summary statistics will be presented for both absolute values and change from baseline for all haematology parameters by previous treatment group, scheduled visit, feeder study and overall DIUR-006 study. Shift tables of baseline to minimum and maximum on-treatment will be produced for the appropriate parameters displaying the number and percentage of subjects in each of the categories (High, Low and Normal) relative to the category of their baseline assessment. Haematology results considered clinically significant by the investigator will be summarised. Detailed listings will be produced for all haematology parameters. In addition, boxplots of change from pre-Chronocort® baseline in haematology parameters over time will be produced along with a line connecting the mean change through time.

For the purpose of both Listings and Summary Tables, the haematology results will be divided into the following groups of related items:

Haematology (1)

- Red blood cell count (RBCs)
- haemoglobin (Hb)
- haematocrit (Hct)

Haematology (2)

- red cell distribution width (RDW)
- mean corpuscular volume (MCV)
- mean cell haemoglobin (MCH)
- mean cell haemoglobin concentration (MCHC)
- platelet count (PLTs)

RDW-CV(%) will be provided by the central laboratory. If any local laboratories provide RDW-SD (fL) measurements, RDW-CV(%) will be calculated from the RDW-SD (fl) and MCV measurements using the formula:

• RDW-CV(%) = (RDW-SD(fL)/MCV)*100.

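### Locally assayed 17-OHP and A4 results would be scored on fixed limits and subtracted from earlier baselines, with no laboratory flag and no central-only repeat of the tables

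*SAP*

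**What the plan says.** **Where hormones may be measured.** The default in Protocol 11.2 is "All laboratory analyses will be carried out by the central laboratory", with local processing for urgent safety results. Protocol 11.11 adds a COVID-19 provision covering six-monthly visits and titrations: "Safety and endocrine blood sampling can also be performed locally if required". It continues: "If local laboratories are used, then normal ranges and certification of the local laboratories will be required". Sponsor approval is needed before any of these measures is used.

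**How the SAP treats local results.** For routine safety tests the rule is explicit: "For the local lab data, the local reference ranges will be used" (SAP 11.4.2, with the same rule for biochemistry in 11.4.3). There is no counterpart for 17-OHP and A4:

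- Responder status (SAP 13.2.1): "A subject will be considered a responder (i.e. disease controlled) if their 09:00 results are in the optimal range for 17-OHP", and separately if A4 is within its normal range; both are repeated for 13:00. The limits are those of "Table 8: Optimal range for 17-OHP and normal reference range for A4". The 17-OHP range is "1.2- 36.4 nmol/L" and rests on clinician feedback. The A4 ranges are sex-specific Mayo Clinic limits.
- SDS (SAP 9.2.2): every result is scaled by the constants in "Table 3: Mean and SD of normal log-transformed range".
- Change scores (SAP 9.3.2 and 13.2.2): the subtracted value is the pre-Chronocort baseline, and for absolute values also the Visit 1 baseline. No condition on laboratory is stated.

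SAP 14 treats the pandemic's effect on these hormones as a missing second sample at US home visits. SAP 10.3.1 summarises delayed visits and missed assessments. The planned repeats of 17-OHP and A4 tables leave out extreme cases; none is limited to central results.

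**The concern.** The A4 endpoint is defined by a normal range, and the protocol requires a local laboratory's normal range to be supplied. The SAP then does not say what that range is for. A local A4 result can lie inside its own laboratory's range and be scored as uncontrolled, or the reverse. Change in SDS and in absolute values has a separate weakness: a local result minus a baseline from another laboratory contains any assay difference as well as any true change.

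Local results under Protocol 11.11 would fall in the later part of follow-up, and the study has no control arm. Long-term control is what the secondary endpoints describe, so a laboratory effect there could be read as a gain or loss over time unless the results are identified and set aside in a comparison table.

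**Working it through.** **1. The SDS scale, reproduced.** Inputs are the SAP Table 2 limits L and U. Mean = (ln L + ln U)/2; SD = (ln U − ln L)/4.

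| | L–U (nmol/L) | Mean | SD | SAP Table 3 |
|---|---|---|---|---|
| 17-OHP male | 1.2–6.7 | 1.042 | 0.430 | 1.042 / 0.430 |
| 17-OHP female | 1.2–8.6 | 1.167 | 0.492 | 1.167 / 0.492 |
| A4 male | 1.4–5.2 | 0.993 | 0.328 | 0.993 / 0.328 |
| A4 female | 1.0–7.0 | 0.973 | 0.486 | 0.973 / 0.486 |

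All eight entries agree. The scale depends only on these limits and does not adapt to the laboratory.

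**2. Shift in the log score.** Assume a local assay reads (1 + b) times the central one. The documents give no b; the range −30% to +30% is an assumption. The signed score moves by ln(1 + b)/SD. For male A4 at b = +20%: 0.182/0.328 = 0.56.

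| b | 17-OHP male | 17-OHP female | A4 male | A4 female |
|---|---|---|---|---|
| −30% | −0.83 | −0.72 | −1.09 | −0.73 |
| −10% | −0.25 | −0.21 | −0.32 | −0.22 |
| +10% | +0.22 | +0.19 | +0.29 | +0.20 |
| +30% | +0.61 | +0.53 | +0.80 | +0.54 |

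The SAP's SDS is unsigned, so direction varies. Take b = +20% in a male. True A4 of 4.0 goes from (1.386 − 0.993)/0.328 = 1.20 to (ln 4.8 − 0.993)/0.328 = 1.75, a rise. True A4 of 2.0 goes from |0.693 − 0.993|/0.328 = 0.91 to |ln 2.4 − 0.993|/0.328 = 0.36, a fall.

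**3. What the Table 8 limits become in central-assay units.** Effective limit = limit/(1 + b).

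| Limit (nmol/L) | b = −30% | −20% | +20% | +30% |
|---|---|---|---|---|
| 17-OHP upper 36.4 | 52.0 | 45.5 | 30.3 | 28.0 |
| A4 male upper 5.2 | 7.43 | 6.50 | 4.33 | 4.00 |
| A4 male lower 1.4 | 2.00 | 1.75 | 1.17 | 1.08 |
| A4 female upper 7.0 | 10.0 | 8.75 | 5.83 | 5.38 |

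At +20%, a male with true A4 between 4.33 and 5.2 is scored uncontrolled, while one between 1.17 and 1.4 becomes controlled. The two ends partly offset.

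**4. Responder rate with no true change.** Assume lognormal values with median m at the upper limit or half of it, log SD s of 0.6 or 1.0, and every result at the visit local. Then P(b) = Φ([ln U − ln m − ln(1 + b)]/s) − Φ([ln L − ln m − ln(1 + b)]/s), with L and U from Table 8.

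- Example: 17-OHP, m = 36.4, s = 0.6, b = −30%. Φ(0.357/0.6) = 72.4% against 50.0%, a gain of 22.4 points.
- b = ±10%: 17-OHP moves 3 to 7 points; A4 moves 0 to 7.
- b = ±30%: 17-OHP moves 8 to 22 points; A4 moves 1 to 22.
- Male A4 with m = 2.6 and s = 0.6 starts at 72.5% and falls either way: by 9.6 points at −30% and 3.2 at +30%.

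For a mixed visit, multiply by the local share. At an assumed 10% share, 22.4 points becomes 2.2.

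**5. Timing.** Enrolment closed on 31 October 2018 (Protocol 11.8). With first dose on that date, 11 March 2020 (the pandemic start in SAP 11.2) is study day 498, inside the Month 18 window of 464–632 (SAP Table 7). Protocol version 15.0 of 17 August 2020, which added Section 11.11, is day 657, in the Month 24 window. For an assumed first dose on 15 August 2016 the same dates are days 1305 and 1464, in the Month 42 and Month 48 windows. The baselines used for change scores therefore precede the provision, and local results under it fall mainly from about Month 18 onward.

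**The case against.** The strongest reply is that the problem may never have arisen. Protocol 11.11 mainly permits local sampling. Local assay is conditional and needs prior approval, and the SAP describes US home visits only as sample collection. The count of locally assayed hormone results may be zero. This stands, and it makes the point conditional.

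Other parts of the reply also stand:

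- A local normal range would be the wrong yardstick for 17-OHP, because the SAP deliberately replaces the normal range with a wider optimal range. The parallel with safety tests holds for A4 only. Even there it concerns classification: change from baseline in safety tests is not adjusted for laboratory either.
- Entry was staggered, so March 2020 falls anywhere from about Month 18 to Month 42, and many visits would mix results from before and during the pandemic.
- The endpoints are descriptive and secondary. Extreme values go to the Data Review Meeting, a partial safeguard.

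A reader might infer that late changes in disease control are laboratory artefacts, or that they could never be separated from true change. The documents support neither. They do not show that a switch took place. Central results arrive electronically (Protocol 14.6) and urgent local ones go into the eCRF (Protocol 11.2), so the source should largely be recoverable. A reader might also infer that a baseline mismatch alters responder status. It cannot, because that status uses no baseline.

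What remains is that the protocol foresees local laboratories and the SAP plans no flag, count or comparison for them. COVID-19 is also not the only route: urgent local results at unscheduled visits (Protocol 11.1.12) can enter an analysis window under SAP 9.3.1.

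**Conclusion.** The concern holds in conditional form. If any 17-OHP or A4 results were assayed locally, the SAP as written could misclassify A4 control and add an assay difference to changes in SDS and absolute values, mainly from about Month 18. The 17-OHP responder rate would also be exposed, because its fixed limit is applied whatever the assay.

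The size is unknown. It depends on the number of local results, the between-laboratory difference and the hormone distribution, none of which the documents give. The figures above are illustrations under stated assumptions, and the direction is not determined because SDS is unsigned and both range limits move. With no local assays the effect is nil.

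One limit on this reading: the text of SAP 8.3 was not in the copy available. The revision history describes its 17-OHP and A4 sensitivity analyses as excluding extreme cases, and the table list agrees. This is a worthwhile correction to descriptive secondary analyses; it does not bear on the safety objective.

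**What to change.** Follow the precedent in SAP 13.4, where a DEXA scanner change leaves all data in the main table and adds a repeat without post-change data. In SAP 9.2.2, 13.2.1 and 13.2.2:

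1. Flag the analysing laboratory for each 17-OHP and A4 result in the dataset and listing.
2. Report the number of locally assayed results by visit.
3. Keep all results in the main tables. Dropping local results there would add missing data at visits already short of samples.
4. Repeat the disease-control, SDS and change-from-baseline tables on centrally analysed results only. Samples taken locally but analysed centrally stay in.
5. Add a sensitivity classification of local A4 results by the local normal range. Keep the fixed optimal range for 17-OHP.

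The cost is SAP wording, one flag and a few extra tables. If no 17-OHP or A4 sample was assayed locally, a single sentence saying so is enough.

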13.2.2. SDS and absolute values

Change from pre-Chronocort® baseline at each visit in SDS, calculated as described in Section 9.2.2, will be summarised over time by overall DIUR-006 study, feeder study and previous treatment. In addition to presenting change from pre-Chronocort® baseline SDS at 09:00 and 13:00 separately, an arithmetic mean of the SDS at the two timepoints will be calculated and summarised over time by overall DIUR-006 study, feeder study and previous treatment.

Absolute values and change from pre-Chronocort® and Visit 1 baseline in 17-OHP and A4 at each visit at 09:00 and 13:00 will also be summarised over time by overall DIUR-006 study, feeder study and previous treatment. The geometric mean of the 17-OHP measurements at 09:00 over time (by visit) will be plotted along with the 95% confidence intervals for the overall DIUR-006 study. This plot may also be repeated by feeder study and previous treatment if this is deemed appropriate at the Data Review Meeting. These plots will be repeated for 17-OHP measurements at 13:00 and A4 measurements at 09:00 and 13:00. Individual subject profile plots may be produced displaying 17-OHP measurements at 09:00 over time (on a logarithmic scale). These profile plots may be repeated for 17-OHP measurements at 13:00 and A4 measurements at 09:00 and 13:00 if this is deemed appropriate at the Data Review meeting.

The intra-subject/within-subject change from pre-Chronocort® and Visit 1 baseline in 09:00 hours levels of 17-OHP and A4 will be listed by visit. Additionally, the subject-level change from pre-Chronocort® baseline along with the intra-subject arithmetic mean changes by visit shall also be displayed visually in a spaghetti plot for these parameters. The spaghetti plot will present the

Statistical Analysis Plan

Version: 6.0 12 July 2022

subjects in the ascending order of their initial Chronocort® daily dose. If the plot is too crowded to draw any meaningful inference, it will be split by groups of participants (feeder study).

13.3. Bone markers and laboratory assessments of special interest

Changes from pre-Chronocort® baseline at each visit in:

- a. Bone turnover markers serum CTX, osteocalcin (after fasting)
- b. Testosterone (total) by gender, separately
- c. Fasting insulin and blood glucose levels, and HbA1c
- d. hsCRP and PRA

Change from baseline will be calculated at each visit (every 6 months from baseline) and summary statistics will be presented for both absolute values and change from baseline for all biomarkers and laboratory assessments of special interest listed above by previous treatment, visit, feeder study and overall DIUR-006 study. Shift tables of baseline to minimum and maximum on-treatment will be produced for the appropriate parameters displaying the number and percentage of subjects in each of the categories (High, Low and Normal) relative to the category of their baseline assessment. Results considered clinically significant by the investigator will be summarised. Detailed listings will be produced for all biomarkers and laboratory assessments of special interest. In addition, boxplots of change from baseline over time for each bone marker or laboratory assessment of special interest will be produced along with a line connecting the mean change through time.

Tables and figures which report on testosterone levels shall only display results by sex individually.

13.4. DEXA scans

Body composition (DEXA) scans will be performed at baseline for subjects entering from study DIUR-003 and then annually for all subjects, except in Germany. Summary statistics will be produced for the absolute values and change from pre-Chronocort® baseline (see Section 9.3.2) for each of fat mass, lean mass, total bone density, T scores and Z scores at each visit.

Due to the length of the study it is possibly that there will be changes in DEXA scanner at some sites. Therefore, the above summary tables will be repeated excluding data post scanner change.

In addition, to explore the potential impact of changes in scanner, an ANOVA 'Analysis of Variance' model will be created to explore whether there is any statistically significant difference in the DEXA results before and after this scanner change. The ANOVA will look at the DEXA scan results (T score and Z score separately and exclusively) at two timepoints: firstly, at the last timepoint for each subject prior to the change in scanner; and secondly at the first DEXA scan for each subject post-scanner change. The response variable in the ANOVA will be the change in the DEXA scan between these two timepoints (ie. the calculated 'post-scanner-result' minus 'pre-scanner-result' for each patient). The ANOVA will use the population of scan result origin as the categorical factor in the analysis: the first level of the population factor will be for 'All subjects' (ie. the Full <Interim> analysis set excluding those subjects with a change in scanner) and the second level of the population factor will be only those Full <Interim> Analysis set subjects who have been exposed to the new DEXA scanner. Using the ANOVA results, the effect size for the difference in mean change between the two populations will be calculated, along with a measure of its statistical significance. These results will be presented in a separate table: 'Change in DEXA scanner results by site population'.

Version: 6.0 12 July 2022

If the difference in mean change between populations is found to be statistically significant at the 5% level, then a second version of the DEXA summary table 'Summary of absolute values of body composition — Dual Energy X-ray Absorptiometry (Full <Interim> analysis set)' will be created exclusively for those parameters, with the subjects' measurements following the scanner change adjusted upwards or downwards by the difference in mean changes between the 'Scanner change' population and the 'All subjects' population from the ANOVA.

In the event of multiple sites changing their DEXA scanners, a separate ANOVA model will be created for each site. Each resulting ANOVA model will continue to compare the 'All subjects' reference results against the site under analysis, but the 'All subjects' set will exclude any data collected from other sites at which the DEXA scanner is changed during the interval between the two timepoints under consideration in the given ANOVA model (ie. the 'All subjects' reference collection used in each ANOVA must compute each patient's change in DEXA scan results between the two timepoints using the same DEXA scanner).

A detailed listing of all DEXA scan results will be produced and will include the date of scanner change and a normal reference flag as described in Section 9.2.4.

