### 5.5 Overview of Chronocort® clinical studies

One Phase I study has been completed to assess the pharmacokinetics (PK) of Chronocort® (study DIUR-002) (Whitaker 2014). Study DIUR-002 fully characterised the PK performance and dose proportionality of Chronocort®. The target PK criteria, commensurate with the endogenous circadian profile for cortisol, were as follows: mean maximum concentration ( $C_{max}$ ) >300 nmol/L (>10.8 mcg/dL) for the 20 mg dose, time taken to reach  $C_{max}$  ( $T_{max}$ ) approximately 6-8 hours post-dosing to prime waking, mean cortisol level >100 nmol/L (>3.6 mcg/dL) up to 16:00 hours, mean cortisol level <100 nmol/L (>3.6 mcg/dL) after 22:00 hours, and relative bioavailability >80%. In study DIUR-002, all assessment criteria were met.

[figure not shown]
Study DIUR-003 (Phase II pilot study) was conducted in 16 subjects at a single site, the (Mallappa 2015). DIUR-003 evaluated the PK profile of cortisol following short-term twice-daily administration of Chronocort® (20 mg at night and 10 mg in morning) in subjects with CAH and this was compared with data from healthy volunteers in the Phase I study. It also examined the effects of both short-term and long-term treatment with Chronocort® on key disease-related biochemical markers and other indices of efficacy/PK. The study evaluated 16 subjects with CAH over a 6-month period. All subjects started the study on 30 mg daily (given as 10 mg at 07:00 and 20 mg at 23:00), with dose titration then taking place within 2 weeks, following investigator review of biochemical and clinical parameters.

The PK profile of Chronocort® after 20 mg at 23:00 and 10 mg at 07:00 in subjects with CAH was similar to that seen in the Phase I clinical study (DIUR-002). The PK profile was characterised by an overnight rise in cortisol levels reaching a maximal concentration approximately 8 hours post-dosing, consistent with the physiological endogenous profile of cortisol reported in normal individuals. The variation in Cmax and area under the curve (AUC) was similar to that seen in physiological cortisol levels in healthy volunteers.

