#### **13.6.2** Efficacy

The total daily dose of Chronocort® in mg/day of hydrocortisone and by BSA will be summarised over time.

Disease control will be based on whether 17-OHP levels are in the optimal range and also whether the A4 levels are in the normal range (both analysed separately). A subject will be considered a responder (i.e. disease controlled) if their 09:00 results are in the optimal range for 17-OHP and then separately if their 09:00 results for A4 are in the normal range. The number and percentage of subjects achieving results in the optimal range will be presented at each visit and by the proportion of dose given at night. This will be repeated for the 13:00 values.

DEXA scans will be performed at baseline for subjects entering from study DIUR-003 and then annually for all subjects, except in Germany. Summary statistics will be produced for the absolute values and change from pre-Chronocort® baseline for fat mass, lean mass, total bone density, T scores and Z scores at each visit. Due to the length of the study, it is possible that there will be changes in the DEXA scanners used at some sites. Therefore, the above summary tables will be repeated excluding data collected after a scanner change and an analysis of variance (ANOVA) model will be created to explore whether there is any statistically significant difference in the DEXA results before and any scanner changes.

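### The DEXA scanner ANOVA isolates a scanner shift only if the changed site and the reference subjects would otherwise have had the same mean change, an assumption the SAP neither states nor protects with covariates

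*SAP*

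**What the plan says.** Protocol 13.6.2 anticipates the problem: "Due to the length of the study, it is possible that there will be changes in the DEXA scanners used at some sites". It provides for the DEXA tables to be repeated without data collected after a change, and for an ANOVA.

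SAP 13.4 gives the detail:

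- **Aim:** to "explore whether there is any statistically significant difference in the DEXA results before and after this scanner change".
- **Outcome:** "The response variable in the ANOVA will be the change in the DEXA scan between these two timepoints", that is, the first scan on the new scanner minus the last on the old one.
- **Factor:** two populations. The reference is the "analysis set excluding those subjects with a change in scanner"; the other level is the "Analysis set subjects who have been exposed to the new DEXA scanner".
- **Parameters:** "T score and Z score separately and exclusively".
- **Several sites changing:** one model per site, with reference changes measured on a single scanner.
- **Consequence:** if the contrast is significant at 5%, the absolute-values table is produced a second time for the affected score, with the values "following the scanner change adjusted upwards or downwards by the difference in mean changes between the" two populations.

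No other term appears in the model.

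**The concern.** The contrast is a difference in differences. Its expectation is the scanner shift plus any difference in the change the two groups would have shown without a switch. The second part is zero only if the groups have equal underlying change. Because the exposed group is one site's subjects, no term in the model can separate the two parts.

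There are reasons in the documents to doubt equal change:

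- SAP 7.2 (Table 1) defines three groups by previous treatment: Chronocort, standard therapy within DIUR-005, and non-study therapy. They start DIUR-006 with different Chronocort exposure, and nothing balances them across sites.
- Protocol 9.1 keeps subjects at their recruiting centre, and DIUR-003 "was conducted in 16 subjects at a single site" (Protocol 5.5). If that site changed scanner, feeder study and scanner change would overlap.
- Protocol 11.2 leaves DEXA technique to each site's usual practice.
- The scan pair is defined by the scanner change, which reference subjects never had. SAP 13.4 does not say which two of their scans to use, so interval and time on treatment may differ between groups.

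At stake is the reading of the adjusted table. A case-mix difference could be presented as instrument drift and subtracted, or a real shift could be masked by an opposite difference in trend.

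**Working it through.** The plan gives no figure to reproduce beyond the 5% trigger: no SD of change, subjects per site or between-site spread. The calculation is therefore conditional.

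**Assumptions (not in the documents).** Within-subject SD of change = 1. The changed site has n = 16 or 10 subjects. The reference has 72 subjects at 9 sites of 8. True site mean changes have SD tau. There is no scanner effect.

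**Formulas.**

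- Variance of the contrast: V = 1/n + 1/72 + tau² × (1 + 1/9).
- Variance the ANOVA believes: (1/n + 1/72) × s², with s² = 1 + 64 tau²/df and df = n + 70 (expected extra between-site sum of squares 8 × 8 × tau²).
- Critical difference: t(0.975, df) × √(believed variance).
- False rejection ≈ 2 × [1 − Φ(critical difference/√V)].

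Example, n = 16 and tau = 0.5. 1/16 + 1/72 = 0.0764 and V = 0.0764 + 0.25 × 1.111 = 0.354, so √V = 0.595. s² = 1 + 16/86 = 1.186. The critical difference is 1.988 × √(0.0764 × 1.186) = 0.598. The ratio is 1.005, giving 31.5%.

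| n | tau | √V | Critical difference | Formula | Simulated (20,000 trials) |
|---|---|---|---|---|---|
| 16 | 0 | 0.276 | 0.549 | 5% (exact t test) | 5.2% |
| 16 | 0.2 | 0.348 | 0.558 | 10.9% | 10.9% |
| 16 | 0.3 | 0.420 | 0.568 | 17.7% | 18.4% |
| 16 | 0.5 | 0.595 | 0.598 | 31.5% | 31.7% |
| 10 | 0 | 0.337 | 0.672 | 5% (exact t test) | 5.2% |
| 10 | 0.2 | 0.398 | 0.682 | 8.6% | 8.8% |
| 10 | 0.3 | 0.462 | 0.695 | 13.3% | 13.9% |
| 10 | 0.5 | 0.626 | 0.736 | 24.0% | 23.8% |

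A second simulation under other assumptions (SD of T-score change 0.3, 10 subjects against 90 at 10 sites) gave 24.2% at tau = 0.15, which is again half the SD.

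**Fixed difference in change.** With 16 against 72, true differences of 0.25, 0.5 and 0.75 SD are rejected 15%, 44% and 76% of the time. These are illustrative inputs.

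**Level differences.** A constant site offset enters both scans and drops out of the change. With a 1.0-unit offset and tau = 0, simulated rejection was 4.8% to 5.7%.

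**When the assumption holds.** With tau = 0, a true shift of 0.3 T-score units (10 against 90, SD 0.3) was detected in 84.5% of runs. The mean estimate among significant runs was 0.33.

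**Size of the applied shift.** With 16 subjects, the mean absolute shift when significant is 0.70 to 0.91 SD for tau 0.2 to 0.5. Much of this is selection on significance: at tau = 0 it is already 0.64, since nothing below about 0.55 can be significant.

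**Precision of a step model.** Each scan has error variance 0.5, because a change has variance 1. For a step judged against a subject's own linear trend, the variance is 0.5/R, where R is the sum of squares of the step left after intercept and time.

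- Six scans split 3/3: R = 1.5 − 4.5²/17.5 = 0.343, SD 1.208, which is 21% larger than 1.
- Four scans split 2/2: R = 1 − 2²/5 = 0.2, SD 1.581, 58% larger.
- Three scans split 2/1: R = 2/3 − 1/2 = 1/6, SD 1.732, 73% larger.

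For the mean of 16 subjects the SEs are 0.30, 0.40 and 0.43 against 0.25.

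**The case against.** The strongest reply is that the design is sound in principle. A plain before/after comparison would count the common time and treatment trend as scanner effect; the reference group removes it. A reader might infer that the ANOVA tests the wrong quantity altogether, or that any difference between sites is subtracted. The documents do not support either reading: under equal change the contrast is the scanner shift, and level differences cancel.

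The safeguards also count. The shift needs p < 0.05, covers T and Z scores only, and goes into an additional absolute-values table beside the unadjusted one. Tables without post-change data are produced for both absolute values and change from baseline, and every scan is listed with the scanner-change date. The secondary endpoint is change from baseline, whose table is not adjusted.

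A reader might also take the single-site DIUR-003 group as a demonstrated case. It is not. No document says that site changed scanner. Sixteen is the maximum eligible, not the number entered. DIUR-005 standard-therapy subjects also start Chronocort at DIUR-006 entry, so the reference contains similar subjects. The scan pair may fall years after entry.

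Finally, tau is assumed, and replacing the ANOVA outright by a step model would cost precision and rest on linear trends.

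All of this stands. It limits the point without removing it: the equal-change assumption is unstated, and the model omits measured variables that bear on it.

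**Conclusion.** The concern holds in a limited form. The SAP 13.4 ANOVA identifies a scanner shift only under equal underlying change, and scanner and site cannot be separated within each model. Differences in change due to previous treatment, time on Chronocort or scan interval can be labelled a scanner effect and removed from the extra T/Z-score table.

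It would be wrong to say the test rejects too often in general. Its error is 5% when sites do not differ in change, and about 9% to 32% only if the between-site SD of change is 0.2 to 0.5 of the within-subject SD with 10 to 16 subjects at the site. The direction follows from the model; the size rests on inputs the documents do not supply. No primary endpoint is affected. The point is worth correcting because it is cheap and because an adjusted table invites being read as the clean one.

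**What to change.** Amend SAP 13.4 as follows:

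1. Add previous treatment (including feeder study), time since first Chronocort dose and the interval between the two scans to the model.
2. For reference subjects, use the scan pair that covers the same interval as at the changed site.
3. Report the estimated shift with its 95% CI, and state the equal-change assumption beside any adjusted table.
4. Where the site has enough annual scans on both sides of the change, add as a sensitivity analysis a mixed model with a step at the scanner-change date, judged against the site's own trend.

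In an illustrative check with unequal case mix, adding previous treatment and time since first dose brought false rejection from 26% to 5%. The 26% reflects the imbalance assumed. Covariates cannot remove unmeasured site differences. If feeder study coincides entirely with the changed site, its term cannot be estimated apart from the scanner, and only item 4 helps.

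The cost is SAP wording, a few degrees of freedom and some precision, using data already collected. The step model is roughly 20% to 70% less precise depending on the number of scans. Subjects enrolled at the October 2018 limit have about 3.3 years to February 2022, so few scans. Protocol 13.8 already allows SAP revision after the Data Review Meeting.
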